## ALLOB-DU1 - Clinical Study Protocol

ALLOB-DU1\_CSP

V 05

Author: [name]

February 02, 2017

Pg. 104/136

- Ineffectiveness, if less than 4 successes are observed
- Efficacy, if 12 or more successes are observed

Otherwise, additional patients will be treated in order to reach a total of 32 patients.

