**Interim Analysis**

A Data Safety Monitoring Board (DSMB) will be established to analyse and report the safety and the efficacy data when 6-month post-treatment results from the first 16 assessable patients will be available. This Board will recommend whether to continue, modify or stop the study. If success is less than 30% or higher than 70%, patient recruitment will be stopped. If the DSMB recommendation is continuation (with or without changes) of the study, patient recruitment will continue until 32 patients have been treated.

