## 2.5 Patient inclusion scheme

With the objective of maximum 32 patients treated in the study, and taking into account 10% drop-out, 35 patients will be enrolled.

For the first 16 patients, the patient recruitment will proceed stepwise by blocks of 4. Full first 2 weeks safety data of the first block of 4 patients will be analysed before the first patient of the second block of 4 patients is treated. First 48 hours safety data of the second block of 4 patients will be analysed before treating the first patient of the next block. This latter scheme will be repeated until the first 16 patients have been treated.

A Data Safety Monitoring Board (DSMB) will be established to assess the safety and efficacy when 6-month post treatment results for the first 16 assessable patients will be available (i.e., interim analysis). This Board will recommend to the Sponsor whether to continue, modify or stop the trial. The study can be prematurely stopped:

- For safety concerns
- For futility if less than 4 successes are observed
- For efficacy if 12 or more successes are observed

Additional patients can otherwise be treated in order to reach a total of 32 patients.

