**8.2.4 Assessment of the Safety Monitoring Committee**

A review of all the reported SAE potentially related to the IMP, and especially those related to immunological reactions (severe AESCs), will be done by the Safety Monitoring Committee

(SMC) after the inclusion of each block of 4 patients until the inclusion of the first 16 patients. This review will cover all SAE potentially related to the IMP from the day of treatment to the first 15 days of follow-up for the first block of 4 patients and from the day of treatment to the end of hospitalization period for the second, third and fourth blocks of 4 patients.

The main conclusions and decisions will be communicated to all Investigators 48 hours after each meeting. A report will subsequently be prepared and its summary submitted to the IECs and CAs. The SMC will be composed by a Safety Consultant and one medically qualified member of the Sponsor. This committee will decide whether the study can be continued as planned. If the decision is to stop or modify the study, it will be communicated by the Sponsor to the Investigators of all centres within 48 hours, the IECs and CAs.

After the review of the fourth block of 4 patients, the recruitment will continue (up to maximum 32 treated patients) and no more safety committee will be performed for all the subsequent treated patients. The safety of all patients will be monitored regularly as described in the study protocol and documented as appropriate.

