## ALLOB-DU1 - Clinical Study Protocol

ALLOB-DU1\_CSP

V 05

Author: [name]

February 02, 2017

Pg. 103/136

- $H_0: p \leq p_0$

- $H_1: p \geq p_1$

Using  $\alpha$  = the type I error and  $\beta$  = the type II error

The tested hypotheses are as follows:

- $H_0$  : a success rate  $\leq 30\%$  is uninteresting ( $p_0=0.30$ )
- $H_1$  : a success rate of at least  $70\%$  is expected ( $p_1=0.70$ )

Using  $\alpha = 0.05$  and  $\beta = 0.20$

In the case of a two-stages Fleming plans, the study can be stopped for ineffectiveness (if the number of successes is lower than a computed limit) or for efficacy (if the number of successes is  $\geq$  a computed limit).

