#### 10.5.8.3 Results of the computing

According to the 2 stages Fleming method, 20 treated patients are required (type I error rate  $\alpha$  of 5% and a statistical power of 80%). Taking into account that patients are enrolled by cohort of 4 and considering the potential heterogeneity of the population, 32 patients in total will be enrolled and treated in the study.

Step	Nb. of patients/step	Cumulated Nb. of patients	Treatment ineffective if $\Pi < 0.30$	Treatment effective if $\Pi > 0.70$
1	16 (assessable)	-	Number of successes $\leq 4$	Number of successes $\geq 12$
2	Up to 16 (assessable)	32	n.a.	n.a.

For the first 16 assessable patients, an interim analysis will be performed at the end of the 6 months follow-up (Visit #6).

The study will be prematurely stopped for:

- Safety concerns

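### The interim futility rule gives two answers at exactly 4 successes out of 16: stop in one place, continue in another

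*Combined protocol and SAP*

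**What the plan says.** The interim analysis covers the first 16 assessable patients at Month 6, and four places state when it leads to a futility stop.

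- **Section 10.5.8.3, table, step 1.** Under a column headed by a success proportion below 0.30, the entry is "Number of successes $\leq 4" (that is, 4 or fewer). The step 2 entries are marked not applicable, so this is the only futility boundary the table gives as a count.
- **Section 10.5.8.3, list under the table.** Introduced by "The study will be prematurely stopped for", the list includes "Ineffectiveness, if less than 4 successes are observed". In any other case further patients are treated, up to 32.
- **Section 2.5.** "For futility if less than 4 successes are observed", introduced by "The study can be prematurely stopped".
- **Synopsis, Interim Analysis.** "If success is less than 30% or higher than 70%, patient recruitment will be stopped".

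Section 10.5.8.2 describes the principle without a number: "the study can be stopped for ineffectiveness (if the number of successes is lower than a computed limit".

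**The concern.** A pre-specified stopping rule has to return one answer for every possible count. Here 4 of 16 falls on the stop side in the table and the synopsis, and on the continue side in the list and in section 2.5. The count is not a remote one: it is among the likeliest interim results if the product does not work. That is the situation the rule exists for, since section 10.5.8.2 justifies the sequential design by limiting how many patients receive an ineffective treatment.

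The study is open and uncontrolled, so interim results can be known to those who decide. If the boundary is ambiguous, the reading can be chosen after the count is seen. The force of the rule is also unclear: 10.5.8.3 and the synopsis say the study or recruitment will stop, while 2.5 and 10.5.8.2 say the study can be stopped.

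**Working it through.** **Inputs.** Stage 1 has 16 assessable patients and the total is 32 (10.5.8.3). p0 = 0.30 and p1 = 0.70 (10.5.8.2). The efficacy stop is 12 or more of 16 (10.5.8.3, 2.5). The candidate futility stops are 4 or fewer (table) and 3 or fewer (list and 2.5).

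**1. Where the table's counts come from.** Apply the 30% and 70% cut-offs to the observed proportion:
- 0.30 × 16 = 4.8, so a proportion below 0.30 means 4 or fewer. Check: 4/16 = 25%, 5/16 = 31.25%.
- 0.70 × 16 = 11.2, so a proportion above 0.70 means 12 or more. Check: 11/16 = 68.75%, 12/16 = 75%.

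Both of the table's counts are reproduced. Fewer than 4 means an observed rate below 25%, a threshold the protocol does not state.

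**2. The general sentence in 10.5.8.2.** A count lower than a limit fits both readings: a limit of 4 gives 3 or fewer, and a limit of 5 gives 4 or fewer.

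**3. Fleming's formula for 16 + 16, one-sided 5% (z = 1.645).**
- Upper bound: round(16 × 0.30 + 1.645 × √(32 × 0.21)) + 1 = round(4.80 + 4.26) + 1 = 10.
- Reference rate for the lower bound: (√(32 × 0.30) + √0.70 × 1.645)² / (32 + 1.645²) = 0.577.
- Lower bound: round(16 × 0.577 − 1.645 × √(32 × 0.577 × 0.423)) = round(4.63) = 5.

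The named method therefore gives stops at 5 or fewer and 10 or more. It supports neither candidate.

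**4. Chance of the disputed count and of a futility stop.** With X ~ Binomial(16, p), at p = 0.30: P(X = 4) = 1820 × 0.30⁴ × 0.70¹² = 0.204.

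| True rate p | P(X = 4) | Stop if X ≤ 4 | Stop if X ≤ 3 |
|---|---|---|---|
| 0.25 | 22.5% | 63.0% | 40.5% |
| 0.30 | 20.4% | 45.0% | 24.6% |
| 0.40 | 10.1% | 16.7% | 6.5% |
| 0.50 | 2.8% | 3.8% | 1.1% |
| 0.70 | 0.02% | 0.03% | 0.003% |

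**5. Expected number treated at p = 0.30.** P(X ≥ 12) = 0.0003, so the chance of continuing is 1 − 0.4499 − 0.0003 = 0.5498 (≤ 4) or 1 − 0.2459 − 0.0003 = 0.7539 (≤ 3; 0.7538 from the rounded terms). Let k be the number already treated beyond 16 when the interim is held. Then expected N = 16 + k + (16 − k) × P(continue). The documents do not give k, so a range is shown:

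| k (assumed) | ≤ 4 | ≤ 3 | Difference |
|---|---|---|---|
| 0 | 24.8 | 28.1 | 3.3 |
| 8 | 28.4 | 30.0 | 1.6 |
| 16 | 32 | 32 | 0 |

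A k above zero is plausible. After the fourth safety block, section 8.2.4 says "the recruitment will continue (up to maximum 32 treated patients", and sections 8.3.4, 10.2 and 10.10 provide for data from patients beyond the first 16.

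**6. Error rates.** P(declare effective) = P(X1 ≥ 12) + the sum over continuing X1 of P(X1) × P(X2 ≥ c − X1), with X1 and X2 ~ Binomial(16, p). The final cut-off c is not given. It is assumed to be the smallest count meeting each stated level: 5% in 10.5.8.2 and 10% in 10.5.1.2.

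| Assumed final cut-off c | Type I error, ≤ 3 vs ≤ 4 | Power at 0.70, ≤ 3 vs ≤ 4 |
|---|---|---|
| 15 of 32 (5% level) | 3.27% vs 3.24% | 99.82% vs 99.81% |
| 14 of 32 (10% level) | 6.92% vs 6.77% | 99.94% vs 99.93% |

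**The case against.** The strongest reply is that little depends on this. Only one of 17 possible interim counts is affected. Type I error and power are almost unchanged, and at the hoped-for 70% rate the count is very improbable. The rule is also not the only safeguard: the DSMB recommends, it can agree changes with the sponsor (10.10), and the sponsor may stop for ineffectiveness (9.4). All of that is correct, and it limits the consequence to the decision at 4 of 16 and at most 3.3 expected patients. It does not tell the DSMB which number to apply.

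Second, the synopsis makes the SAP the only statistical reference, section 10 calls it the main one, and 8.3.4 provides for a DSMB guidance document. The boundary may have been settled there. No separate SAP or guidance text is in the material available, so the contradiction is established for the protocol only.

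Third, preferring 4 or fewer is open to challenge. Section 10.5.8.2 is strict for futility and inclusive for efficacy. Combined with the numbers 4 and 12, that is the form used in the list, so the table's sign could be the slip. Fleming's formula supports neither value. This stands as a reason to ask for the derivation and not to presume the intention. What favours 4 or fewer is its agreement with the 30% threshold in both the table heading and the synopsis.

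**Conclusion.** The contradiction is real and lies in the current text. At exactly 4 of 16, the table and the synopsis stop the study, while the list in 10.5.8.3 and section 2.5 continue it. The two readings differ by 20.4 percentage points in the probability of a futility stop at a true rate of 30%, and by 22.5 points at 25%. These figures rest only on a binomial count in 16 patients. The expected sample size figures also depend on how many patients have been treated by the interim. The error rates depend on an assumed final cut-off, and they barely differ whichever level is used.

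The point must be fixed because a decision threshold has two answers at a likely result, not because the trial's error control fails.

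**What to change.** State one futility count and use it in the synopsis, section 2.5, and both the table and the list in 10.5.8.3.

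- If the 30% threshold on the observed proportion is intended, the count is 4 or fewer of 16, and section 2.5 and the list need rewording.
- If 3 or fewer is intended, the table entry, its column heading and the synopsis percentage need changing.

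In either case, show how the count was derived, since Fleming's formula for 16 + 16 does not give it. State whether the rule is binding and use the same verb throughout. Repeat the wording in the SAP and the DSMB guidance document. All of this should be done before interim data are seen.

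The drafting is small, but section 11.9 requires a protocol amendment to be approved by the authorities and ethics committees before it is implemented. Choosing 4 or fewer also has a statistical price: more futility stops at intermediate true rates (16.7% against 6.5% at 40%, and 3.8% against 1.1% at 50%). At 70% a futility stop stays below 0.1% with either count.

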**Statistical Analysis**

Statistical methods will be exhaustively described in a Statistical Analysis Plan (SAP), which will constitute the only reference document. The SAP will be reviewed, approved, and signed prior to database lock at the latest.

The safety population will be considered as the primary cohort for analysis of efficacy. It will comprise all treated patients.

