#### 10.5.1.2 *Type I error rate, significance tests*

In this study, two sided tests will be performed at a 5% level of significance except for efficacy analyses.

According to the Schoenfeld approach (Schoenfeld *et al.*, 1980), for the efficacy analysis, the type I error rate will be increased from the usual 5% to the 10% rate. Indeed, in this pilot single arm “proof of concept” study, it is appropriate to maintain the power and increase the type I error rate. This increases the risk of erroneously concluding that the treatment is worthy of further investigation, but does not increase the risk of missing an efficacious treatment. So in

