#### **10.7 Sample size estimation**

Using the 2 stages Fleming method, a maximum of 32 treated patients are required. Assuming a rate of 10 % of non-assessable patients, a total of 35 patients will have to be enrolled.

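### The 5% type I error and 80% power in section 10.5.8.3 belong to a 20-patient plan, not the 16+16 plan adopted; that plan has no visible success limit at 32 and contradictory futility limits at 16

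*Combined protocol and SAP*

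**What the plan says.** - **Hypotheses.** Section 10.5.8.2 tests a success rate of at most 30% against one of at least 70%, with alpha 0.05 and beta 0.20.
- **Size.** Section 10.5.8.3 opens with "According to the 2 stages Fleming method, 20 treated patients are required", at a type I error rate "of 5% and a statistical power of 80" per cent. It then raises the total to 32, citing cohorts of four and a heterogeneous population. Section 10.7 credits the larger number to the same method: "Using the 2 stages Fleming method, a maximum of 32 treated patients are required".
- **Limits.** The table in 10.5.8.3 has two steps of 16 assessable patients. Step 1 is ineffective at 4 or fewer successes and effective at 12 or more. Step 2 has n.a. in both columns; this is printed text, not a redaction. The section ends: "Otherwise, additional patients will be treated in order to reach a total of 32 patients".
- **Futility elsewhere.** The synopsis (Interim Analysis) stops recruitment below 30% success. Section 2.5 and the list after the table set futility at fewer than 4 successes.
- **Alpha elsewhere.** Section 10.5.1.2 says "In this study, two sided tests will be performed at a 5% level of significance except for efficacy analyses", and that for efficacy "the type I error rate will be increased from the usual 5% to the 10% rate". It does not say whether the 10% is one- or two-sided.
- **Denominator.** Sections 10.1 and 10.2 count efficacy on all treated patients; the table counts assessable patients.
- **Reference document.** The synopsis says "Statistical methods will be exhaustively described in a Statistical Analysis Plan (SAP), which will constitute the only reference document".

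**The concern.** The error rates of a two-stage plan follow from the stage-1 and final limits together. The quoted pair belongs to a plan that is not being run. For the plan that is being run, the visible text stops at stage 1, so a reader cannot verify its type I error or power. A trial that is undecided at 16 goes on to 32 with no visible statement of what result counts as success. In an open, uncontrolled study that limit should be in writing before the final data are known.

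The futility conflict comes earlier and needs no inference. With exactly 4 successes among the first 16, the monitoring board would find two passages telling it to stop and two that do not.

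**Working it through.** **Inputs.** p0 = 0.30 and p1 = 0.70 (10.5.8.2); n1 = 16, n2 = 16, efficacy at 12 or more (10.5.8.3). Futility is at a or fewer, with a = 3 (section 2.5 and the list) or a = 4 (table, synopsis). All figures are exact binomial and one-sided, with stage-1 limits applied as binding and 16 patients counted at each stage.

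**1. The plan's own figure, N = 20.** The smallest exact single-stage design with at most 5% type I error and at least 80% power has n = 10 (6 or more of 10: 4.7% and 85.0%). The plan gives no stage sizes for its 20 patients. Assuming 10+10 with Fleming-type limits (stop at 3 or fewer, or 7 or more; final 10 or more), type I error is 4.8% and power 97.7%. So 20 fits the 5%, but is not reproduced as the number needed for 80%.

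**2. Stage 1 of the adopted plan.** P(X1 ≥ 12) = Σ C(16,x) p^x (1−p)^(16−x), for x = 12 to 16.
- At p = 0.30: 0.00027, or 0.03%.
- At p = 0.70: 0.4499, or 45.0%.
- The probability of continuing to 32 at p = 0.70 is about 0.55 under either futility limit. At p = 0.30 it is 0.754 (a = 3) or 0.550 (a = 4).

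**3. The whole plan, for a cumulative limit r at 32.** P(success) = P(X1 ≥ 12) + Σ P(X1 = x) · P(X2 ≥ r − x), for x = a+1 to 11.

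| r of 32 | Type I error (a = 3 / a = 4) | Power at 0.70 |
|---|---|---|
| 14 | 6.9% / 6.8% | 99.9% |
| 15 | 3.3% / 3.2% | 99.8% |
| 20 | 0.04% | 87.4% |
| 21 | 0.03% | 79.1% |

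The least limit that keeps one-sided 5% is 15. Fleming's formula agrees: 32 × 0.30 + 1.645 × √(32 × 0.30 × 0.70) = 13.86, rounded to 14, plus 1 = 15.

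**4. Sidedness of the 10%.** Two-sided 10% equals one-sided 5% and leads to 15. One-sided 10% leads to 14. The choice changes the conclusion only when a trial continues and ends at exactly 14 of 32: 3.5–3.7% of trials at p = 0.30, at most about 14% near p = 0.45, and 0.1% at p = 0.70.

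**5. The futility conflict.** 30% of 16 is 4.8, so below 30% means 4 or fewer, as in the table. Fewer than 4 means 3 or fewer. The readings differ at X1 = 4:
- p = 0.30: 1820 × 0.0081 × 0.01384 = 0.204.
- p = 0.40: 0.101.
- p = 0.70: 0.0002.

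The efficacy side agrees throughout: 70% of 16 is 11.2, so above 70% means 12 or more.

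**The case against.** The best defence is that the final limit is probably set somewhere. Lines are blacked out directly after the responder definition in 10.5.6.1 and in 10.5.9, and section 10 says that the protocol's description is not exhaustive and defers to a SAP signed before database lock. The n.a. may mean only that no further early stop applies. The stated method, p0, alpha and total lead to 15 of 32 without further input. The move from 20 to 32 is explained, and this is a pilot study.

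Much of that stands, and it rules out three stronger readings.

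- **That the trial has no final criterion.** The visible text cannot show this; it shows only that the criterion is not printed where the limits are tabulated.
- **That power is only 45%.** That is the chance of stopping early for efficacy at a 70% rate, a floor and not the power of a completed plan. With 15 of 32, power is 99.8%.
- **That any limit from 15 to 20 is equally open.** All six meet 5% and 80%, and a result of 15–19 of 32 would fall between them in 58% of trials at p = 0.50 and 47% at p = 0.60. That is an outer bound only. It treats 20 of 32, with a type I error of 0.04%, as a natural choice in a plan whose section 10.5.1.2 prefers to relax type I error. On the natural reading only 14 versus 15 is open.

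The defence does not reach the printed contradictions. Redaction or a SAP cannot reconcile 4 or fewer with fewer than 4, or make error rates quoted for 20 patients those of a 16+16 plan. A reason for enlarging the trial does not explain why one section says the method requires 20 and another 32.

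**Conclusion.** The point holds as a should-fix. Confidence is high on the printed contradictions: the futility limit (20% of trials at a true rate of 30%, 10% at 40%), 20 against 32 patients, and 5%/80% quoted for a plan not adopted. Confidence is moderate on the missing final limit, because it may be set in redacted text or in the SAP.

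On the visible text the adopted plan fixes only floors, 0.03% type I error and 45.0% power. If 15 of 32 is intended, both stated targets are met comfortably and the sample size is adequate. These figures assume 16 counted patients per stage and binding stage-1 limits.

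**What to change.** 1. State one stage-1 futility number and use it in the synopsis, section 2.5, the table and the list after it.
2. Replace the step-2 n.a. with the cumulative limit, or cite where it is already set. At one-sided 5% the least exact limit is 15 or more of 32 (type I error 3.2–3.3%, power 99.8%, under either futility number).
3. Replace the 5%/80% statement for 20 patients with the exact figures for the 16+16 plan, and align 10.5.8.3 with 10.7 on the number required.
4. State in 10.5.1.2 that the 10% is two-sided, which matches the one-sided 5% of 10.5.8. If it is one-sided, the limit is 14 or more of 32 (6.8–6.9%, 99.9%).
5. Reconcile the denominator: all treated (10.1, 10.2) or assessable (table).

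The cost is protocol and SAP wording, settled before the final data are seen. No extra patients or data are needed.

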#### **10.5.9 Post-treatment data analysis**

The final CSR including assessment of both efficacy and safety endpoints, will be established at 6 months.

[REDACTED]

[REDACTED]

[REDACTED]

[REDACTED]

#### **10.6 Randomisation**

There is no randomisation in the study.

#### **10.7 Sample size estimation**

Using the 2 stages Fleming method, a maximum of 32 treated patients are required. Assuming a rate of 10 % of non-assessable patients, a total of 35 patients will have to be enrolled.

#### **10.8 Handling of missing values**

For all efficacy criteria, the imputation approach will incorporate the pattern of missing values as follows:

- Missing data due to treatment-related AE leading to study withdrawal will be replaced by the Worst Observation Carried Forward (WOCF) method from scheduled or unscheduled visits: for each patient dropping out due to treatment related AE, his/her worst observation will be used to replace his/her missing values.

## ALLOB-DU1 - Clinical Study Protocol

ALLOB-DU1\_CSP

V 05

Author: [name]

February 02, 2017

Pg. 105/136

- Missing data due to any reason other than treatment-related AE leading to study withdrawal will be imputed using last observation carried forward (LOCF) from previous visit (scheduled or unscheduled visit).
- Missing values in-between two measured values will be extrapolated using linear mixed models.

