## 2 INVESTIGATIONAL PLAN

### 2.1 General Study Design

The present study is a prospective, multicentre, open, non-controlled study to assess the safety and efficacy of allogeneic osteoblastic cells (ALLOB®) implantation in non-infected delayed-union fractures.

After signing the Informed Consent Form (ICF), enrolled patients will enter an up to 8 weeks screening period. Eligible patients (according to the eligibility criteria) will be treated by a single ALLOB® implantation into the delayed-union site. Once treated, patients will be followed up during 6 months with post-treatment assessments performed: at 2 weeks, 1, 3 and 6 months, respectively. During follow-up, non-responding patients (see below and section 3.2.3) could be considered as drop-out and undergo a rescue surgery, according to the judgment of the Investigator.

[REDACTED]

[REDACTED]

[REDACTED]

Experimental design	Prospective, multicentre, open, non-controlled Phase I/IIa study
Duration of study	6 months of follow-up
Delayed-union sites	Femur, tibia, fibula, humerus, ulna, radius
Treatment	ALLOB ®
Procedure	Implantation performed under anaesthesia
Study Timepoints	2 weeks, 1 month, 3 months and 6 months after treatment

Self-contained study

Data collection: Case Report Form (CRF)

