#### 2.2.4 Consideration for Rescue Surgery

During the study follow-up, if judged necessary, the Investigators will have the possibility to withdraw the patient from the study for a rescue treatment such as a bone autograft or any other appropriate surgical or non-surgical treatment. In this case, an early discontinuation visit will be scheduled. Reasons for rescue surgery will be documented.

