#### **2.3.2.2 *Rescue Surgery Procedure***

When judged necessary, the Principal Investigator can decide to perform a rescue surgery. The patient can be withdrawn from the study for a rescue surgical (e.g., bone autograft, allograft...) or non-surgical treatment according to the standard-of-care procedure of the investigating site.

Reason for rescue surgery, type and date will be recorded.

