## ALLOB-DU1 - Clinical Study Protocol

ALLOB-DU1\_CSP

V 05

Author: [name]

February 02, 2017

Pg. 91/136

the patient and documented in source documentation and the CRF. Particularly, the patient must be carefully questioned for the possible occurrence of any AE or SAE.

- *Lack of compliance to the protocol*

The Sponsor has the right to terminate the study at any time.

- *Lost to follow-up*

Intensive efforts will be made to re-contact patients who do not return for scheduled visits in order to, at minimum, determine health status and the potential occurrence of AE and/or SAE. All efforts to re-contact will be documented in the source documentation and the CRF.

- *Lack of efficacy*

Early discontinuation for lack of efficacy will not be considered as an AE but as a treatment failure. The reason of the lack of efficacy will be documented in the CRF and source documents.

- *Other reasons*

If no above-mentioned reasons are applicable in case of early discontinuation, the other reason(s) will be clearly documented and explained in the CRF and source documents.

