## 9.3 Replacement of Subjects

Patients withdrawn from the study will not be replaced.

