### 10.1 Analysis Populations

Two analysis sets will be defined:

- The safety population that will include all treated patients. (Treated patients will be defined as patients implanted with ALLOB®). As the study is not randomized and only one study group will be studied, the safety set will be used also to analyse the whole efficacy data.
- The Per-Protocol (PP) efficacy population will include all patients of the safety population without any major protocol deviation.

The definition of the populations will be finalised prior to database lock. The safety population will be considered as the primary cohort for the analysis of safety, efficacy, demographics, and baseline characteristics. Efficacy variables will be analysed using the safety population. Primary criteria and corresponding variables will be analysed in the PP population.

The patients screened will be described in the summary table presenting the disposition of patients.

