#### **10.5.6 Efficacy analysis**

##### **10.5.6.1 Primary efficacy criteria**

The primary efficacy criteria will be analysed in the safety population and in the PP population, the safety population corresponding to the main efficacy population.

Percentage of responder patients will be calculated as the percentage of patients who will not be considered as failed under treatment at Month 6.

A patient will be considered as failed under a treatment if, at Month 6:

- He/she had a rescue surgery

Or

- The Global Disease Evaluation score (VAS) as perceived by the patient has not improved by at least 25% *and* the TUS as assessed by CT scan has not increased by at least two points (versus baseline).

[REDACTED]

[REDACTED]

[REDACTED]

[REDACTED]

[REDACTED]

ALLOB-DU1 - Clinical Study Protocol

ALLOB-DU1 CSP

V 05

Author: [name]

February 02, 2017

Pg. 100/136

A series of horizontal black bars of varying lengths, likely representing a redacted list of items. The bars are arranged vertically and have irregular, jagged ends, suggesting they are cut-off fragments of a larger list. The lengths of the bars vary significantly, with some being very short and others being quite long.

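### In the visible text, withdrawal for lack of efficacy is a treatment failure in section 9.1, but the endpoint definition omits it and section 10.8 imputes it by LOCF, so such a patient can be scored a success

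*Combined protocol and SAP*

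**What the plan says.** Five places state the primary failure rule in the same way: the synopsis (Efficacy Endpoints) and sections 2.2.2, 10.2, 10.5.6.1 and 10.5.8.1. There are two routes to failure at Month 6. The first, in the words of 10.5.6.1, is "He/she had a rescue surgery". The second requires both a GDE improvement below 25% and a TUS gain below 2 points. Withdrawal for lack of efficacy is not listed.

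Section 9.1 lists reasons for early discontinuation. Under lack of efficacy it says: "Early discontinuation for lack of efficacy will not be considered as an AE but as a treatment failure". It sets no threshold and does not require surgery.

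Section 10.8 covers all efficacy criteria. Withdrawals for a treatment-related adverse event receive worst observation carried forward (WOCF). For everything else: "Missing data due to any reason other than treatment-related AE leading to study withdrawal will be imputed using last observation carried forward (LOCF").

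Every treated patient has to be scored. Section 10.1 states that "the safety set will be used also to analyse the whole efficacy data", and 9.3 that "Patients withdrawn from the study will not be replaced".

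On rescue, section 2.1 says that "non-responding patients (see below and section 3.2.3) could be considered as drop-out and undergo a rescue surgery". Section 2.2.4, whose heading speaks of rescue surgery, allows withdrawal for "a rescue treatment such as a bone autograft or any other appropriate surgical or non-surgical treatment". Section 2.3.2.2 has a similar heading and says: "The patient can be withdrawn from the study for a rescue surgical (e.g., bone autograft, allograft...) or non-surgical treatment".

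**The concern.** Two visible rules can give opposite primary-endpoint results for the same patient. Section 9.1 assigns failure because of why the patient left. Sections 10.2 and 10.8 together look only at the last recorded values, and one threshold met is enough to avoid failure. If 10.8 is applied as written, patients whose treatment was judged not to work can be counted as responders. Any resulting bias in the success rate is upward.

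This matters because the trial is small, open and uncontrolled, with a binary endpoint and interim stopping rules based on counts out of 16. The ordering is also odd: 10.8 gives the conservative imputation to treatment-related adverse-event withdrawals, while withdrawals that 9.1 already calls failures receive the more lenient one.

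**Working it through.** **Inputs**
- Failure rule (10.2): rescue surgery, or GDE improvement below 25% together with TUS gain below 2 points.
- GDE (2.4.2): 0 is best and 100 worst, so improvement = (baseline − last) / baseline. The entry floor is 20 mm (2.6.2).
- Month-3 switch criteria (3.2.3): GDE improvement below 15% and TUS or mRUS improvement below 1 point.
- Interim boundaries (10.5.8.3): efficacy at 12 or more of 16. Futility is 4 or fewer in the table, but fewer than 4 in the text there and in 2.5.

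**Step 1: score example patients withdrawn for lack of efficacy.** The patient values are illustrations. The last values are carried to Month 6.
- GDE 40 to 28 mm, TUS unchanged, no rescue surgery: (40 − 28)/40 = 30%. Success under 10.2 with 10.8; failure under 9.1.
- GDE 20 to 15 mm, TUS unchanged, no rescue surgery: (20 − 15)/20 = 25%. The same conflict, on a change of 5 mm. Section 3.2.1 gives 8 to 12 mm as the minimally important difference.
- GDE unchanged, TUS 6 to 8, no rescue surgery: the same conflict, but only if a CT was done between baseline and withdrawal. The visit schedule is blacked out, so the visible text does not show whether one would be.
- GDE 60 to 52 mm, TUS 6 to 6: (60 − 52)/60 = 13.3%. Failure under both rules.
- Any values, with rescue surgery: failure under both rules.

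**Step 2: bound the group.** A patient who meets the Month-3 switch criteria, with TUS as the radiological score, is below 15% and 1 point. That patient is therefore also below 25% and 2 points, and fails either way. The conflict is left with patients withdrawn for lack of efficacy, without rescue surgery, and with one threshold met. This group is not empty by rule:
- 2.2.4 and 2.3.2.2 let the investigator withdraw a patient on judgement, including for non-surgical treatment.
- 3.2.3 notes that clinical and radiological improvement do not always go together.

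**Step 3: size per patient.**
- 1/16 = 6.25 points at the interim; 1/32 = 3.1 points at the end.
- At the efficacy boundary, one reclassified patient turns 11/16 into 12/16.
- At the futility boundary, it turns 4/16 into 5/16 (table version) or 3/16 into 4/16 (text version).

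**Step 4: can such a patient be among the interim 16?** The definition of an assessable patient admits someone who completed only Visit #5. The synopsis asks for 16 completed patients, and 2.2 speaks of assessable patients who have reached the 6-month visit. Inclusion is unsettled, so the interim effect is conditional. The final analysis is affected in any case.

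**The case against.** The best case on the other side has four parts.

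- **Section 9.1 may not be a scoring rule.** It introduces a list of reasons to be documented in the CRF, and the sentence mainly separates lack of efficacy from adverse events. It mentions neither Month 6 nor the endpoint, which is worded consistently in five places. This reading is possible. But 9.1 uses the term treatment failure without limit, and nothing tells the person scoring the endpoint to disregard it.
- **The rules can coexist.** A patient already classed as failed has no missing responder status to impute. This is the sensible order, but the visible text does not state it.
- **The group is very small.** This stands. If rescue surgery is an umbrella term that includes non-surgical rescue, the group shrinks further.
- **Unseen text may settle it.** This also stands. The synopsis makes the SAP the only reference document for statistical methods, that separate SAP is not in the text supplied, and part of 10.5.6.1 is blacked out.

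A reader might infer that the conflict distorts the trial's error rates or stopping probabilities by a known amount. The documents do not support that, because they give no frequency for such patients. Suppose exactly one is among the 16 and the other 15 succeed independently at the null rate of 30%. The chance of 4 or fewer successes is then 51.5% if the patient is scored a failure and 29.7% if scored a success. With fewer than 4, it is 29.7% against 12.7%. Any single reclassified patient would produce these shifts, so they say nothing particular about this rule. The chance of an efficacy stop in the same setting is 0.01% against 0.07%.

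A reader might also infer that the endpoint must already count non-surgical rescue as failure, or must exclude it. Sections 2.2.4 and 2.3.2.2 suggest an umbrella term, but the endpoint wording does not settle it either way.

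**Conclusion.** The point holds as an unresolved conflict in the visible text between 9.1 on one side and 10.2 with 10.8 on the other. It concerns patients withdrawn for lack of efficacy without rescue surgery whose last GDE is at least 25% better, or whose TUS is up at least 2 points if a CT preceded withdrawal. The effect is limited to the per-patient shifts above, with the interim shift depending on inclusion among the 16.

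The conclusion assumes that 9.1 can be read as assigning outcome status and that neither the SAP nor the blacked-out text gives the order of precedence. It is worth correcting because the written imputation rule favours success and the protocol already assigns these patients a status. Confidence is medium.

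**What to change.** - In the synopsis and sections 2.2.2, 10.2, 10.5.6.1 and 10.5.8.1, state that discontinuation for lack of efficacy is scored as failure before any imputation, consistent with 9.1.
- In 10.8, limit LOCF and WOCF to the values still missing after that step.
- Separately, reconcile the endpoint term rescue surgery with 2.2.4 and 2.3.2.2, and state for scoring purposes which treatments it covers. This need not change when or how rescue is given.
- If the SAP already contains these rules, align the protocol wording with it. Section 10 allows the SAP to be signed as late as the first database lock, so the order of precedence should be fixed before outcomes are reviewed.

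The cost is a few sentences, with no new data, visits or analyses. The reported success rate may be slightly lower, and some failures will rest on the investigator's recorded reason for withdrawal in an open study.
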